## BACKGROUND

Ewing sarcoma, commonly bearing a pathognomonic *EWS-FL1* translocation, is the second most common bone malignancy in children and adolescents, with an annual incidence of 200–500 cases in the United States and of 120-150 cases in Italy [1,2]. With advances in multidisciplinary care, 5-year survival rates for pediatric Ewing sarcoma patients have improved from 50% during the period from 1983–1990 to 70% during the period from 2004–2016 [1-3]. Prolonged disease-free survival is achieved in the majority of patients with localized Ewing sarcoma after treatment with multiagent chemotherapy and primary tumor control [3]. The best predictive factor is histologically determined chemotherapy-induced necrosis assessed in resected primary tumors, that has allowed to identify patients who are candidates for more intensive or novel therapies [3-6]. The good and poor responder patients to neo-adjuvant chemotherapy has been defined to different systems published in literature: true Percentage, Huvos System and Bologna System [4-7].

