## OBJECTIVE OF THE STUDY

The aim of the present study is to evaluate which is the best scoring tool to determine the histological response to chemotherapy in localized Ewing sarcoma of bone.

The study will exam all the different systems to evaluate the histological necrosis after neo-adjuvant chemotherapy in all patients with localized Ewing sarcomas of bone surgically treated between 1982 and 2012.

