## POPULATION

### Inclusion criteria

- 1) Male and female patients surgically treated at Rizzoli Institute from 01 Jan 1982 to 31 Dic 2012
- 2) Patients with diagnosis of Ewing sarcoma of bone who have had neo-adjuvant chemotherapy
- 3) Diagnosis of Ewing sarcoma localized

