**Exclusion criteria**

1. Metastatic disease at presentation
2. Soft tissue origin
3. Radiotherapy before surgery

The study will include male and female patients without limit of age

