**STATISTICS**

To the case series will be applied a descriptive statistic.

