**DATA COLLECTION**

Clinical data will be retrieved by patient charts.

A protocol-specific CRF reporting the results of the review will be provided.

A CRF is required and should be completed for each included subject.

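### Does treatment guided by histological response bias the comparison of the three scoring systems?

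*Protocol*

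**What the plan says.** - Background: after calling necrosis in the resected tumour the strongest predictor, the protocol adds "that has allowed to identify patients who are candidates for more intensive or novel therapies", citing published work. It then lists the candidates for comparison: "different systems published in literature: true Percentage, Huvos System and Bologna System".
- Objective of the Study: the aim is to "evaluate which is the best scoring tool to determine the histological response to chemotherapy in localized Ewing sarcoma of bone", "in all patients with localized Ewing sarcomas of bone surgically treated between 1982 and 2012". No criterion for the best tool is given, and no survival endpoint is named.
- Population: the inclusion criteria cover patients "surgically treated at Rizzoli Institute from 01 Jan 1982 to 31 Dic 2012". The only treatment-related exclusion is "Radiotherapy before surgery".
- Statistics: "To the case series will be applied a descriptive statistic". That is the whole section.
- Data Collection: "Clinical data will be retrieved by patient charts", entered on a protocol-specific case report form whose items are not listed. Material and Methods adds that all medical records will be reviewed and that about 500 cases are expected.

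Treatment after surgery is nowhere named as a variable, stratum or restriction, and nowhere excluded as one.

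**The concern.** Read together, the Background and Statistics sections suggest a familiar trap. A marker that clinicians act on loses apparent prognostic value when the action works. If poor responders on system A received effective extra treatment, A's outcome difference between good and poor responders narrows. System B, which nobody acted on, narrows less, because its poor group includes patients who were not intensified. The distortion falls unequally on the tools being ranked, and a larger series does not remove it. At stake would be the study's main conclusion: a less accurate system could be named best because the more accurate one had been used.

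**Working it through.** The protocol gives no effect size, power or sample-size derivation, so there is no figure to reproduce. The check has three parts: what the text supports, how strong the mechanism would have to be, and whether stratifying by later treatment would cure it.

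**1. The premises the bias needs**

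| Premise | What the protocol says |
|---|---|
| Patients in this series were treated according to response | Not stated. The Background speaks of identifying candidates, in general and with references |
| One of the three systems made that decision | Not stated |
| The systems are ranked on outcome after surgery | Not stated. The Objective speaks of determining histological response |
| The analysis ignores later treatment | Not stated. Descriptive results can be tabulated by treatment or era |
| Later treatment is not recorded | Not stated. Charts are reviewed and the form's items are not listed |

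The phrase about all patients in the Objective defines the population. It does not commit the study to an unstratified comparison.

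**2. Size of the mechanism if the first three premises were true**

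From the protocol: n = 500, and 5-year survival between 50% and 70%. Everything else is assumed. In both models A is the better system and guides treatment, and h is the hazard ratio of the intensified treatment.

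*Model 1.* Half the patients are true poor responders (L = 1). A classifies 90% correctly and B 80%. T = 1 for A-poor patients who are intensified. The yearly hazard is 0.045 × 3^L × h^T, with 10 years of follow-up and 200 runs per setting. Without a treatment effect, 5-year survival is 0.5 × exp(−0.045 × 5) + 0.5 × exp(−0.135 × 5) = 0.5 × 0.799 + 0.5 × 0.509 = 0.65, inside the protocol's range.

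*Model 2.* Response is a latent normal variable with log hazard 0.6 per SD. A and B are good/poor splits with noise SD 0.4 and 0.8. Log(h) is added for treated A-poor patients, with censoring at 5 years. There were 300 runs per setting at full uptake. The partial-uptake settings used 1,000 runs and an assumed baseline hazard of 0.09 per year.

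Share of simulated studies in which the worse system B ranks first on concordance (– means not run):

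| h | Model 1, 100% uptake | Model 1, 50% | Model 2, 100% uptake | Model 2, 50% | Model 2, 25% |
|---|---|---|---|---|---|
| 1.0 | 4% | 4% | 20% | about 19% | about 19% |
| 0.8 | 17% | 10% | 45% | 29% | 21% |
| 0.7 | 40% | 14% | 60% | 36% | – |
| 0.6 | 61% | 20% | 73% | 43% | 30% |
| 0.5 | 80% | 33% | – | 56% | 35% |
| 0.4 | 97% | 53% | – | – | – |

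The first row is chance alone. With full uptake, mean concordance (A versus B) crosses between h = 0.7 and 0.6 in Model 1 (0.564 vs 0.560, then 0.547 vs 0.550). In Model 2 it crosses between 0.8 and 0.7 (0.580 vs 0.577, then 0.562 vs 0.566). At 50% uptake, Model 1 only draws level at h = 0.4 (0.556 vs 0.556), and in Model 2 B comes out ahead more often than not only at about 0.5. At 25% uptake there is no reversal in the range tested.

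Full uptake means that one system decided treatment for every poor responder over 2012 − 1982 + 1 = 31 calendar years. Nothing in the protocol suggests this.

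**3. Would stratifying by postoperative regimen help?**

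Not in the full-uptake case, where the bias is largest. There the regimen is identical to A's classification, so within each regimen A takes a single value and its concordance is 0.50 by construction. B keeps about 0.54 and ranks first in 97–100% of runs, even when treatment has no effect (h = 1.0). This failure is specific to full uptake, but it shows that the obvious adjustment is no general safeguard.

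**The case for a change.** The strongest case for the concern is that outcome is the natural reading of the aim. The Background values necrosis for its predictive power, the study reviews clinical as well as histological data, and no histological reference standard is named against which a scoring tool could be judged. On that reading, both models agree that effective response-guided treatment always costs the guiding system something. In Model 1 at full uptake and h = 0.7, its 5-year survival gap falls from about 23 to 12 points, while the rival's falls from about 18 to 12. No analysis plan can stratify on a variable that was never captured, and the charts are being opened anyway.

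What stands is the direction of the effect, and a modest conditional suggestion: if the systems are compared on outcome, and if response decided treatment in this series, it would be useful to know each patient's later treatment and to look separately at patients whose treatment did not depend on response.

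What does not stand is the step to a defect in this document. Outcome as the criterion is an inference; agreement or reproducibility between the scores would be untouched by later treatment. Response-guided treatment in this series is a second inference. That the form omits later treatment is a third, since its items are not shown. Covariates, strata and restricted analyses are also what a protocol commonly leaves to the analysis plan.

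**Conclusion.** The concern does not hold. The protocol does not say that response selected treatment in this series, does not say which system was used, and does not fix an outcome ranking or an analysis blind to treatment. The alleged bias rests on premises supplied from outside the text. What remains is silence on a matter that an unseen analysis plan and case report form may cover.

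On size, a moderate treatment effect is not enough by itself. On the assumed inputs, reversal of the average ranking needs a hazard ratio of about 0.6 to 0.7 with every poor responder on one system intensified, or about 0.4 to 0.5 at half uptake. If treatment had no effect or was not guided by response, there is no penalty at all. These thresholds depend on the assumed accuracies, the strength of the prognostic effect and the follow-up. Only the sample size and the survival range come from the protocol. The conclusion would need another look if the analysis plan or case report form showed both an outcome-based ranking and treatment decided by one of the three systems.

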## OBJECTIVE OF THE STUDY

The aim of the present study is to evaluate which is the best scoring tool to determine the histological response to chemotherapy in localized Ewing sarcoma of bone.

The study will exam all the different systems to evaluate the histological necrosis after neo-adjuvant chemotherapy in all patients with localized Ewing sarcomas of bone surgically treated between 1982 and 2012.

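### Does pooling 31 years of surgery (1982–2012) under a purely descriptive plan confound the comparison of the necrosis scoring systems?

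*Protocol*

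**What the plan says.** The inclusion criteria admit patients "surgically treated at Rizzoli Institute from 01 Jan 1982 to 31 Dic 2012", and the Objective describes the same series, with the systems examined "in all patients with localized Ewing sarcomas of bone surgically treated between 1982 and 2012". Metastatic disease, soft-tissue origin and radiotherapy before surgery are excluded. There is no age restriction: "The study will include male and female patients without limit of age". About 500 cases are expected (Material and Methods).

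The aim is to find the best tool for determining histological response to chemotherapy. The Background names three systems: true percentage, Huvos and Bologna. The Objective gives no criterion for best and names no survival endpoint.

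The Statistics section is one sentence: "To the case series will be applied a descriptive statistic". Under Data Collection, "Clinical data will be retrieved by patient charts". No section mentions period of surgery or chemotherapy protocol as an analysis factor.

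Two statements in the Background bear on the question. Five-year survival rates in pediatric Ewing sarcoma "have improved from 50% during the period from 1983–1990 to 70% during the period from 2004–2016". On necrosis: "The best predictive factor is histologically determined chemotherapy-induced necrosis assessed in resected primary tumors".

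**The concern.** The window covers 31 calendar years, and the protocol's own Background links calendar time to outcome by a 20-point rise in survival. It also presents necrosis as a predictor, so it is natural to read the best system as the one that best separates survivors from non-survivors.

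On that reading, suppose good responders became more common over the same years. Good responders would then come disproportionately from the later, better-surviving period, and a score with no prognostic value within any period would still show a survival difference when the years are pooled. A system whose good-responder share drifted more than another's would gain more from this and could be ranked too high. With only a descriptive analysis named, nothing in the text guards against that.

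**Working it through.** **1. What the protocol fixes.** The window is 2012 − 1982 + 1 = 31 years. The protocol derives no sample size, power or effect size, so there is no calculated figure to reproduce; 500 is an expected count. The Objective and inclusion criteria define eligibility. The Statistics sentence limits the analysis to description, and results tabulated by period of surgery are description. No sentence commits to a pooled-only result.

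**2. What would have to be true for the ranking to be biased.**

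- (a) Best is judged by separation of outcome. The protocol does not say so. The stated aim concerns determining histological response, and agreement or reproducibility is another possible criterion.
- (b) This cohort has a material survival gap by era. The 50% and 70% figures are for pediatric Ewing sarcoma in general, and the later period runs to 2016. This cohort is localized, operated, of bone origin and of any age. For 14 of its 31 years (1982 and 1991–2003) the Background gives no survival figure.
- (c) The share of good responders changed over time. No data are given.
- (d) It changed differently between the systems. No data are given, and the systems grade the same patients.

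Conditions (a) to (c) distort the apparent strength of a single score. The ranking needs (d) as well.

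**3. Size for a single score.** Assume two equal eras with survival s1 and s2, good-responder shares g1 and g2, and no score effect within an era:

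- good = (g1·s1 + g2·s2)/(g1 + g2)
- poor = ((1−g1)·s1 + (1−g2)·s2)/((1−g1) + (1−g2))

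Example with s = 50%/70% and g = 30%/50%: good = (0.15 + 0.35)/0.8 = 62.5%; poor = (0.35 + 0.35)/1.2 = 58.3%; difference 4.2 points.

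The gradual model uses equal yearly numbers, survival of 50% to 1990 rising linearly to 70% in 2004 and flat after, and a share changing linearly over 1982–2012. All shares are assumptions.

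| Good-responder share, early to late | Eras 50%/70% | Eras 55%/65% | Gradual |
|---|---|---|---|
| constant | 0 | 0 | 0 |
| 30% to 40% | 2.2 | 1.1 | 1.1 |
| 30% to 50% | 4.2 | 2.1 | 2.0 |
| 20% to 70% | 10.1 | 5.1 | 4.9 |

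For scale, with 500 cases, 40% good responders and 60% survival, the standard error of one score's good-minus-poor difference is √(0.24/200 + 0.24/300) = 4.47 points. Only the 20% to 70% drift exceeds it, and it does so in all three columns.

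**4. Size for the ranking.** Take one system going from 30% to 50% (4.17 points) in the 50%/70% two-era model and subtract the other system's spurious difference:

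- other also 30% to 50%: 4.17 − 4.17 = 0
- other 40% to 60%: 4.17 − 4.00 = 0.17
- other 20% to 30%: 4.17 − 2.67 = 1.50
- other constant at 30%: 4.17 − 0 = 4.17, or 2.0 in the gradual model

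Sharper drifts give larger gaps. A system going from 30% to 70% shows good (0.15 + 0.49)/1.0 = 64% against poor (0.35 + 0.21)/1.0 = 56%, a difference of 8 points, while a constant-share system shows 0. If both systems truly separate survival by 20 points within each era, the same pair reads 24.8 and 20.0, a gap of 4.8.

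The 4.47-point standard error does not apply to these gaps, because two systems scored in the same patients are correlated.

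**5. What stratifying costs.** With 60% survival and equal good and poor groups, the 95% half-width is 1.96·√(0.24/250 + 0.24/250) = 8.6 points for 500 cases, and 1.96·√(0.24/125 + 0.24/125) = 12.1 points for each of two periods of 250. If later chemotherapy improved survival by improving necrosis, stratified results would also understate a score's total separation.

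**The case for a change.** The strongest case for the concern is that the era–outcome link comes from the sponsor's own Background, that prognostic value is the most natural meaning of best, and that bias, unlike sampling error, does not shrink with 500 cases. Date of surgery is already needed to establish eligibility, so a display by period would cost little. One sentence in the Statistics section would bring it in, with the pooled result kept alongside.

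Much of this stands as advice. The facts about the window and the one-line Statistics section are correct, the arithmetic reproduces, and a breakdown by period would be sensible if scores are compared with survival. It does not turn the protocol's text into an error. The request is to announce a stratification and display choice that commonly belongs in a statistical analysis plan, and the protocol leaves that choice open. The outcome comparison at risk is inferred from a background statement. The missing criterion for best is a separate question, and era confounding follows from only one possible answer to it.

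**Conclusion.** The concern does not hold. The protocol sets an eligibility window and a descriptive approach; neither is wrong, neither contradicts the other, and neither prevents results by period.

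The ranking of the systems would be biased only if all four conditions in the working held together, and the documents establish none of them. In the four comparisons against a system moving from 30% to 50%, the spurious gap is 0 to 4.2 points with an abrupt 20-point era change, and the 4.2 becomes 2.0 when the change is gradual. The 8-point and 4.8-point gaps come from a sharper assumed drift set against no drift at all in the same patients.

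These sizes rest wholly on assumed responder shares and on borrowed pediatric survival rates, so they show what could happen and do not estimate this series. Showing results by period is a reasonable preference for the analysis plan, at some cost in precision and with the interpretive caveat about necrosis.

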## STUDY DESIGN

This is single institution cases series review of histological and clinical data

## POPULATION

### Inclusion criteria

- 1) Male and female patients surgically treated at Rizzoli Institute from 01 Jan 1982 to 31 Dic 2012
- 2) Patients with diagnosis of Ewing sarcoma of bone who have had neo-adjuvant chemotherapy
- 3) Diagnosis of Ewing sarcoma localized

**Exclusion criteria**

1. Metastatic disease at presentation
2. Soft tissue origin
3. Radiotherapy before surgery

The study will include male and female patients without limit of age

**MATERIAL AND METHODS**

We will retrieve from the database of the Rizzoli institute all the cases with a histological diagnosis of Ewing sarcoma from 01 Jan 1982 to 31 Dic 2012.

We expect to find approximately 500 cases.

We will review all the medical records, and histological data of these cases.

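### Does searching by diagnosis date while selecting by surgery date, with a stated 500 cases, leave the series incomplete or its size overstated?

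*Protocol*

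**What the plan says.** The protocol attaches the same calendar window to two different events. The Objective refers to "all patients with localized Ewing sarcomas of bone surgically treated between 1982 and 2012", and the first inclusion criterion agrees: "Male and female patients surgically treated at Rizzoli Institute from 01 Jan 1982 to 31 Dic 2012". Material and Methods describes the database search as "all the cases with a histological diagnosis of Ewing sarcoma from 01 Jan 1982 to 31 Dic 2012".

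The search is also broader than the population. It is not limited to bone, to localized disease or to operated patients. The Population section adds those limits, together with "Patients with diagnosis of Ewing sarcoma of bone who have had neo-adjuvant chemotherapy", and excludes "Metastatic disease at presentation", "Soft tissue origin" and "Radiotherapy before surgery".

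The only number of patients in the protocol comes directly after the search sentence: "We expect to find approximately 500 cases". The next sentence says that the records of those cases will be reviewed. No expected number of eligible patients is given. The Statistics section plans descriptive statistics only.

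**The concern.** There are two worries.

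**Dates.** Eligible patients have chemotherapy between diagnosis and operation. If the search uses the date of first diagnosis, someone diagnosed late in 1981 and operated on in 1982 meets the inclusion criteria but is never retrieved, and later screening cannot bring that patient back. The Objective claims all such patients, so the search would not quite deliver what it promises.

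**Count.** The 500 describes every Ewing sarcoma diagnosis found. Metastatic cases, soft-tissue tumours, patients irradiated before surgery and patients never operated on must come out. A reader who takes 500 as the size of the analysed series would expect more precision than the study will have. Because the aim is to compare systems that sort patients into response groups, precision within groups is what would suffer.

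**Working it through.** **The plan's own figure.** The 500 cannot be reproduced by a formula. It is an expected database count, with no significance level, power, effect size or precision target behind it.

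**Date mismatch**

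Inputs from the protocol: 500 cases; a window from 01 Jan 1982 to 31 Dec 2012, which is 31 years or 372 months. Assumptions, because the protocol gives no figures: even accrual, a gap of 2 to 6 months from diagnosis to surgery, and an eligible share of 50% to 90% of retrieved cases.

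- Rate: 500 / 31 = 16.1 cases per year.
- Cases in the gap at one edge: 16.1 × 2/12 = 2.7, and 16.1 × 6/12 = 8.1.
- As a share of the series: 2/372 = 0.5%, and 6/372 = 1.6%. This share does not depend on how many cases are eligible.
- Eligible patients missed: 2.7 × 0.50 = 1.3 at the low end, 8.1 × 0.90 = 7.3 at the high end.

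The two edges differ:

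| Patient | Meets the surgery window? | Retrieved, if the date is first biopsy? | Result |
|---|---|---|---|
| Diagnosed late 1981, operated 1982 | Yes | No | Missed |
| Diagnosed late 2012, operated 2013 | No | Yes | Removed at screening |

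Only the first row loses anyone. If the search date is that of the histology report on the resected tumour, both windows refer to the operation and nobody is missed.

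**Largest possible effect on a proportion.** If a fraction f of eligible patients is missing, a proportion in the full series differs from the observed one by f × (missing − observed), which cannot exceed f. At f = 1.6% the shift is at most 1.6 percentage points, and only if the missing patients were entirely unlike the rest. Sampling error alone is larger. The 95% half-width for a 50% proportion, 1.96 × √(0.25/n), is:

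- n = 500: 4.4 points
- n = 450: 4.6 points
- n = 250: 6.2 points

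**Count**

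Eligible number = 500 × eligible share. Assumed shares of 90%, 70% and 50% give 450, 350 and 250. A larger drop is possible; the protocol has no exclusion rates from which to choose.

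For precision within groups, take 65% survival in four equal groups, neither of which is in the protocol. The half-width 1.96 × √(0.65 × 0.35 / (n/4)) is 8.4 points at n = 500, 9.3 at n = 400 and 13.2 at n = 200. These figures show how precision falls with n. They do not show that a statement in the protocol is wrong, because it makes no statement about precision.

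**The case for a change.** The strongest case for a change is that the text does not match itself and would be cheap to repair. The same dates are tied to two successive events, the protocol does not say which histology report is meant, and two people running the search could return slightly different cohorts. The number of cases likewise belongs to a wider set than the one studied, and the expected eligible number is absent.

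The wording mismatch stands. What does not stand is the consequence. Every eligible patient was operated on and must have a response read on the resected tumour, so a search of histology records can find that patient through the resection report as well as the biopsy. On the strict reading the loss is a handful of patients at one edge, chosen by calendar date and not by response or outcome. They are absent from every scoring system at once, and no mechanism is apparent by which that would favour one system over another.

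On the count, the complaint defeats itself. If 500 is the number retrieved, the protocol says so and overstates nothing. If the authors meant 500 eligible cases, there is again no overstatement, only a loosely placed sentence. What remains is that an eligible number is not given. In a review of existing records that number is fixed by the archive once the criteria are applied, and forecasting it would change neither who is included nor what is done with them.

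**Conclusion.** No change is needed. The difference between diagnosis date and surgery date is a real looseness in wording, and whoever runs the search can settle it by applying the surgery window that both the Objective and the inclusion criteria state. Taken literally, it costs about 1 to 7 eligible patients, or 0.5% to 1.6% of the series. That rests on even accrual, a gap of 2 to 6 months and, for the patient numbers, 50% to 90% eligibility, none of which the protocol supplies. If accrual around the start of 1982 were twice the average, the share would be 1.1% to 3.2%, still small. On the resection-report reading the loss is nil.

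The analysed series will be smaller than 500 to the extent that retrieved cases fail the criteria. By how much cannot be told from the protocol, but no stated operating characteristic depends on it. Reporting how many cases were retrieved, excluded and analysed is ordinary practice when the series is written up.
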